434 to contact the subject. These attempts will include at least 1 certified mail receipt. If all attempts
435 to contact the subject fail, that subject will be considered to be lost to follow-up and discontinued
436 from the study.

437

438 *Protocol violation*: The subject's laboratory or other findings, or the subject's conduct, fail to
439 meet the protocol entry criteria or fail to adhere to the protocol requirements. Subject pregnancy
440 or intention of becoming pregnant would also be a violation.

441

442 The Stopping Criteria for individual subjects include:

443

444 The Principal Investigator, study physician, and/or nurse practitioner conclude it is unsafe for the
445 subject to continue. These reasons may include:

- 446
- 447 • A new diagnosis is made of a significant medical condition which could influence the
response to liraglutide (e.g., renal failure).
 - 448 • A medication is begun that could alter the subject's responses to liraglutide.

449

450 Subjects meeting individual stopping criteria will be withdrawn from the trial.

451

452 **Subject Replacement**

453

454 Subjects who prematurely discontinue from the study or become ineligible will not be replaced
455 once they have been randomized.

456

[figure not shown]
457 **Visit Procedures**

458

459 Figure 1 shows the flow of subjects through randomization. Table 1 presents the schedule of
460 study assessments and treatment visits.

461

462 Figure 1. Study Flow Diagram

463
464 **Screening Procedures**
465
466 All applicants will be screened by phone and questions administered through REDCap (the
467 University of Pennsylvania's research data capture system) to determine whether they potentially
468 meet eligibility criteria. We will obtain a waiver of written documentation of consent for the
469 telephone and electronic questionnaire screen. Those who appear to meet eligibility criteria and
470 remain interested in the trial will be scheduled for an in-person interview.
471

472 The in-person interview will be conducted by a psychologist or Masters' level staff member,
473 who will obtain informed consent and evaluate subjects' behavioral eligibility (i.e., willingness
474 and appropriateness to participate). Individuals who do not wish to participate in the research
475 study will receive recommendations for alternative treatments for binge eating disorder if they
476 are interested. Assessment of eligibility will include examination of the applicants' BED

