724 measures across the two treatment groups will be compared using appropriate 2-sample tests,
725 including Wilcoxon rank-sum and t-tests for continuous variables, and Fisher's exact and Pearson
726 Chi-square tests for categorical variables. Any baseline variables found to be associated with
727 treatment condition will be added to the outcome analysis as a covariate.

728
729 **Primary analysis.** The primary outcome is the degree of reduction in binge episodes per week.
730 It is count data that is likely to be skewed, so a shifted log transformation will be considered to
731 stabilize the distribution to better meet the normality assumptions. To address the primary aim 1,
732 a mixed effects model will be fit with Treatment Group (liraglutide 3.0 mg/d and placebo) as a
733 between subjects factor and Time (Weeks 1 through 17) as a categorical within-subjects factor.
734 Time is treated as a categorical factor so that we can use the group-time interactions with the
735 time main effect to estimate and test intention-to-treat (ITT) treatment group differences at each
736 time point, with the 17-week time point as our primary ITT test. In fitting a mixed effects model
737 with maximum likelihood, a variance-covariance structure must be selected. We will begin by
738 assuming a compound symmetry structure, but also consider criteria such as the Akaike's
739 Information Criterion (AIC) for selecting the best form of the variance-covariance structure
740 using Residual Maximum Likelihood (REML) (e.g., Compound Symmetry, Toeplitz, first-order
741 autoregressive, and unstructured). Furthermore, we will include as baseline covariates those
742 variables that have been established to be associated with the outcome based on prior literature,
743 including sex and age. The results from the mixed model will be summarized by mean (SE)
744 change from baseline for each treatment group at each time point.
745

746 Given the above definition of the ITT tests under the mixed effects model, the main interest in
747 this study is the to the test of the primary hypotheses that participants randomized to liraglutide
748 3.0 mg/d (N=76) will show superior improvements from baseline to treatment end (week 17) in
749 the number of binge episodes per week as compared to those on placebo (N=76). The primary
750 hypothesis will be evaluated at the alpha = 0.05 level and all other contrasts and

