783 *administered at each visit and can be included in the proposed models.*

784
785 **Safety analysis.** Given the modest sample size, we will not perform safety analysis. Instead,
786 safety labs will be reviewed on an individual basis with participants to assure that they are within
787 normal limits, and these will be available in summary for publications/presentations. The details
788 for reporting SAEs to the IRB and procedures for taking action to safeguard participants are
789 described in the safety monitoring plan.

790
791 **Missing data and statistical models.** Every effort will be made to obtain follow-up data on all
792 participants randomized. Based on prior studies that we have conducted, the dropout rate by 17
793 weeks could be as high as 15%. Our maximum likelihood approach assumes that any missing
794 outcome data are missing at random (i.e., missing data, including those due to drop-out, but not
795 dependent on any previously observed outcomes or treatment assignment). With this approach,
796 we will use all data that have been collected, without regard to whether data are missing for a
797 participant at another visit, including drop-out, and without explicit imputation of missing data.
798 We will conduct sensitivity analyses to examine the impact of missing data. Details regarding
799 the sensitivity analyses will be pre-specified prior to unblinding. Furthermore, we will assess
800 whether dropout status or level of compliance is associated with treatment condition as well as
801 baseline demographic variables using appropriate 2-sample tests, including Wilcoxon rank-sum
802 and t-tests for continuous variables, and Fisher's exact and Pearson Chi-square tests for
803 categorical variables, and all findings will be reported.

804
805 Change in frequency of binge episodes per week also will be analyzed using a per protocol
806 analysis that, for liraglutide-treated participants, includes only those who were able to tolerate
807 and adhered to the full dose of liraglutide 3.0 mg.

808
809 **Interim Analysis**

810 No interim analyses are planned (in order to maintain full power for the end-of-study
811 comparisons).

812
813 **Explorative Statistical Analysis for Pharmacogenetics and Biomarkers**

814 No explorative statistical analysis for pharmacogenetics and biomarkers will be performed.

815
816 *5.20.19 Of note, due to unforeseen low response to advertising and the mis-allocation of*

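### Participants who meet a stopping criterion leave the trial itself and no later binge assessment is planned, which sits badly with the commitment to follow everyone randomised and with the week-17 ITT test

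*Combined protocol and SAP*

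**What the plan says.** Withdrawal Criteria lists what may lead the study team to judge it unsafe for someone to continue. Two examples are given, both events after randomisation: "A new diagnosis is made of a significant medical condition which could influence the" response to liraglutide, and "A medication is begun that could alter the" response to it. The consequence follows: "Subjects meeting individual stopping criteria will be withdrawn from the trial". The same section records reasons for stopping early, adverse events among them, as reasons for leaving the study and not only the drug.

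Under Missing data and statistical models the commitment is: "Every effort will be made to obtain follow-up data on all" randomised participants. The Primary analysis paragraph estimates ITT group differences at each "time point, with the 17-week time point as our primary ITT test". The missing-data paragraph adds that "we will use all data that have been collected, without regard to whether data are missing for a" participant at another visit, with no explicit imputation. It assumes that "outcome data are missing at random (i.e., missing data, including those due to drop-out, but not" related to earlier outcomes or to arm. Sensitivity analyses for missing data are promised, with details to be fixed before unblinding.

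**The concern.** An ITT comparison at week 17 needs week-17 outcomes from everyone randomised, including those who stopped drug. If meeting a stopping criterion ends trial participation, those outcomes are not collected, and no analysis can recover them. The reasons for stopping arise after randomisation and may be linked to arm or to how the participant is doing. The group difference would then depend on what the model assumes about people it never saw off drug. With 36 participants in place of the planned 152, each lost week-17 value also carries more weight.

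**Working it through.** **1. Is there any planned off-drug binge assessment?** The places where one could appear are:

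- Table 1 and Assessments for Efficacy: binge interviews take place at study visits through week 17. There is no early-termination visit and no retained week-17 visit for people who have been withdrawn.
- Withdrawal Criteria, lost to follow-up: the repeated contact attempts apply to people who do not return and cannot be reached.
- Data Handling: vital status is sought after authorisation is revoked.
- Follow-up of Adverse Events, and Pregnancy: medical care and pregnancy outcomes.

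None of these collects binge data after drug is stopped. The note under Analyses for Aim 3 points the same way. It says that the Eating Inventory scales, scheduled only at baseline and week 17, exist for completers alone. That concerns a questionnaire and not the binge interview, but it suggests that non-completers were not assessed at week 17.

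**2. What the model does with the gap.** Visits before withdrawal stay in the likelihood. The week-17 value of someone who left is in effect predicted from that person's earlier visits and from people in the same arm who stayed. Those data are mainly on treatment, so the estimate moves towards an on-treatment effect. The plan names missing at random but describes missingness unrelated to earlier outcomes or arm, which is closer to missing completely at random. Removal on safety grounds may breach that description.

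**3. What determines the bias.** In each arm let p be the share withdrawn under this rule. Let g be the gap between the model's implied week-17 reduction for them and their actual reduction. Then

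bias in the difference (liraglutide minus placebo) = p_L × g_L − p_P × g_P.

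The documents give none of these four quantities. For scale only, assume 18 per arm (the split of the 36 is not stated) and a gap of 1.6 episodes per week, the planning difference. One such liraglutide participant adds 1.6 / 18 = 0.09 to the estimated difference, and one such placebo participant subtracts 0.09. Equal shares and equal gaps cancel.

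**4. The attrition figures available.** The plan's own calculation reproduces. The SD of the mean of 10 visits with ICC 0.59 is 4.1 × √[(1 + 9 × 0.59)/10] = 3.257. A difference of 1.6 then needs 65.04, so 66 per arm or 132 in total (power 80.6%), and 132 × 1.15 = 151.8, so 152. The 15% in that calculation is dropout from all causes.

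The May 2019 note gives, among participants unaffected by the misallocation, 5 non-completers and 1 completer in the first year. In the second year it gives 15 with usable data: 1 lost to follow-up, 4 complete and 10 active. That is 6 losses among 6 + 15 = 21. No stopping criterion is mentioned for any of the 6, and their arms are not given.

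**The case against.** The commitment is to make every effort, not to obtain complete data, and the same paragraph expects dropout. No sentence forbids a week-17 assessment after withdrawal, so the loss is inferred from the lack of any procedure. This stands: it is a tension to reconcile, and a reader who infers that the two statements cannot both hold goes too far.

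A reader might also infer a size. Multiplying the planning effect by dropout gives 0.15 × 1.6 = 0.24, or (6/21) × 1.6 = 0.46 episodes per week. The documents do not support this. Both rates cover all causes and pool the arms, and the calculation assumes that every liraglutide leaver loses the whole benefit while placebo leavers have no gap. The second rate is also unstable: the same six are 6/36 = 17% of the analysis set, and 6/11 = 55% of unaffected participants whose outcome was known. Even 0.24 to 0.46 is only 0.18 to 0.34 of a simple week-17 standard error of 4.1 × √(2/18) = 1.37, assuming 18 per arm.

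A third inference is that the bias favours liraglutide through poor tolerability. Tolerability is not among the listed stopping examples. Difficulty during escalation is met by a delayed escalation, and a newly started medication can occur in either arm. The direction is not established.

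The plan does keep data from before withdrawal, does promise sensitivity analyses, and will report whether dropout is associated with arm. These help, but the sensitivity analyses have no stated content and cannot replace outcomes that were never collected.

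**Conclusion.** The point holds as a gap in data collection that weakens the ITT claim. The stopping rule takes people out of the trial, and nothing in the documents provides binge outcomes afterwards. Any week-17 estimate for those people rests on an assumption the data cannot test, and the result lies closer to an on-treatment effect than to the effect in everyone randomised.

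The size and direction of bias are unknown, because neither the number meeting a stopping criterion nor their arms are reported. The conclusion rests on one inference: that withdrawal from the trial, with no off-drug procedure, means no week-17 interview. The sample-size figure is not in dispute. No view is taken on the clinical criteria themselves. The change is worth making, but its practical reach was limited once recruitment had stopped.

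**What to change.** Reconcile Withdrawal Criteria with the missing-data paragraph. Leave the stopping criteria exactly as they are, and state that meeting one ends study drug and does not by itself end follow-up. Unless the participant withdraws consent, continue the binge interviews already scheduled through week 17 and include those data in the ITT mixed model. Report the number meeting a stopping criterion in each arm.

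The cost is an amendment and some staff time for interviewing people off drug. The visits are already in the schedule. If telephone interviews were wanted they would be a new procedure for efficacy data, since the plan uses the telephone for binge reports only in the run-in. Outcomes already lost may not be recoverable. At the May 2019 note the change could help only those of the 10 active participants who later met a criterion.

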564 described later (see Assessment for Efficacy).

565

566 Following randomization, all subjects will have a medical visit with the study physician or nurse
567 practitioner who will instruct them in the use of liraglutide 3.0 (as described later) and provide
568 the first month's supply of medication.

569

570 Subjects will be provided liraglutide 3.0 (Saxenda) or placebo after being randomized at week 0.
571 Liraglutide 3.0, a glucagonlike peptide-1 receptor agonist, is a once-daily self-administered,
572 subcutaneous injection [42]. Liraglutide 3.0 mg or placebo will be provided as pre-filled,
573 disposable, personal injectors. Subjects will be taught (by the study physician or nurse
574 practitioner) how to properly perform subcutaneous injections into their abdomen, thigh, or
575 upper arm. In addition, subjects will be given an instruction card about how to administer the
576 medication. To reduce the likelihood of gastrointestinal symptoms (e.g., nausea, vomiting), the
577 medication will be initiated at 0.6 mg daily for 1 week, and then increased by 0.6 mg/day in
578 weekly intervals until a dose of 3 mg/day is achieved (please see below for dosing schedule).
579 Subjects will be instructed that if they miss a dose, to resume the once-daily regimen with the
580 next scheduled dose and not to take an extra dose or higher dose. If subjects miss more than 3
581 days, they will be instructed to contact the physician or nurse practitioner who will initiate
582 therapy at 0.6 mg/day to avoid gastrointestinal symptoms. Subjects who do not tolerate an
583 increased dose during escalation will have a delayed dose escalation by up to 7 days. Study
584 medical staff also will help subjects develop a medication schedule, based on when and where
585 subjects will take the medication each day and how they will remind themselves to do so.

586 **Figure 2. Dosing Schedule for Liraglutide**

587

Week 1	Week 2	Week 3	Week 4	Week 5 Full Dose
0.6 mg	1.2 mg	1.8 mg	2.4 mg	3.0 mg

588

589

590 After randomization, subjects will return at week 1 to assess rate of response. Subjects will
591 return for study visits every two weeks thereafter, at weeks 3, 5, 7, 9, 11, 13, 15, and 17. Study
592 staff will review the individual's medication adherence at each study visit, determining the
593 number of days that liraglutide was used each week and identifying reasons for missed doses.
594 The number of doses of medication taken each week will be tracked.
595

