660 Diagnostics.) Each blood draw will require approximately 1 tablespoon (i.e., 15 mls) of blood.
661 Blood pressure and pulse will be measured on each occasion using an automated monitor
662 (Dinamap, model 9300). Two readings will be taken on each occasion (at 1-minute intervals),
663 after participants have been seated for at least 5 minutes.

664

665 At baseline screening, participants will complete a history and physical examination and have an
666 EKG. Interpretation of results will use the categories "normal", "abnormal", not clinically
667 significant" or "abnormal, clinically significant". Subjects will be screened extensively (by a
668 physician or nurse practitioner) to determine that they have no contraindications to the use of
669 liraglutide or to possible weight loss.

670

671 **Other Assessments**

672 n/a

673

674 **Subject Compliance**

675 Subjects will be instructed to keep a medication diary to be reviewed at each visit, and they will
676 be asked if they have missed any doses since their last visit. We will also measure subjects'
677 medication adherence using injection counts from visual inspection of the dose counter taken
678 from subjects' injection pens. Subjects will be instructed to bring the pen to each session, and we
679 will record missed doses and problem solve with subjects if they are missing doses.

680

681

682 **Assessing Adverse Events**
683 All information regarding adverse events will be actively collected from the point of the first
684 study-related activity (i.e., completion of the informed consent procedure), through to each
685 participant's study endpoint. This includes adverse events that may be related to any study
686 procedure (i.e., laboratory tests or ECGs) that may not have been performed during normal
687 management of the participant, in addition to his/her use of liraglutide.
688

689 **STATISTICAL CONSIDERATIONS:**

690 **Sample Size Calculation**

691 A power analysis was conducted for the primary outcome, reduction in binge episodes per week
692 (i.e., last 7 days). Estimated variances and clinically relevant treatment differences were derived
693 from the literature using previous randomized controlled trials for BED [14, 45]. The common
694 standard deviation used was 4.1 [45], and the clinically relevant change in binge episode used
695 was 1.6 binge episodes per week [45]. Furthermore, a mixed effects model design assuming a

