696 compound symmetry covariance structure (congruent with the primary analytic plan) with a total
697 of 10 assessment points and an ICC parameter equal to 0.59 (this is the value that was used as the
698 auto correlation rho in PASS), estimated based on data collected from similar populations within
699 our Center for Weight and Eating Disorders [46], i.e., reduction in nocturnal ingestions per week
700 among patients with night eating syndrome with an SSRI. There is often overlap between
701 persons with night eating syndrome and BED and we believe that the variance in improvements
702 from week to week in core symptoms of these disorders would be similar. Based on these
703 estimates, a baseline sample size of 152 participants (76 per group) with a 15% attrition rate
704 (actual total n=132) will give 80% power to detect a clinically relevant mean difference in degree
705 of reduction in binge episodes of 1.6 per week (effect size: 0.39) to be significant at alpha = 0.05,
706 based on a two-sided test. All secondary outcomes will be considered exploratory and evaluated
707 at the alpha=0.05 level. However, those exploratory analyses will provide valuable findings on
708 changes in weight and other clinically meaningful changes in eating disordered attitudes and
709 behaviors that have not been examined previously in relation to the use of liraglutide. The power
710 analysis was conducted using the PASS software, Version 11 NCSS LLC, Kaysville, UT [47].
711

712 **Statistical Methods**

713 Preliminary and descriptive analyses. All data will first be assessed for missing and out-of-range
714 values with basic statistical procedures such as univariate statistics (means, confidence intervals,
715 standard deviations, ranges, frequencies, proportions, percentiles) and graphs such as histograms,
716 box and whisker plots, scatter plots and Q-Q plots. All questions of data quality will be
717 investigated and resolved before any statistical modelling, as complete and accurate data are
718 essential for unbiased estimates and confidence intervals.
719

720 Baseline and demographic characteristics will be summarized overall for all subjects and by
721 treatment group. Means and confidence intervals will be provided for continuous variables and
722 frequencies and percentages for categorical variables. Graphical methods mentioned above will
723 be used to examine distributions and identify potential influential points. The balance of baseline

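### The stated 80% power at n=132 matches a difference averaged over visits, not the primary week-17 contrast; with SD 4.1 that contrast has about 61% or 70%, reaching 79–80% only with baseline adjustment, and nothing is restated for n=36

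*Combined protocol and SAP*

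**What the plan says.** Under Statistical Considerations, Sample Size Calculation, variances and differences are taken "from the literature using previous randomized controlled trials for BED [14, 45]. The common" "standard deviation used was 4.1 [45], and the clinically relevant change in binge episode used" is 1.6 episodes per week. The calculation assumes compound symmetry with a total "of 10 assessment points and an ICC parameter equal to 0.59", entered in PASS as the autocorrelation. The result is given as "estimates, a baseline sample size of 152 participants (76 per group) with a 15% attrition rate", and "actual total n=132) will give 80% power to detect a clinically relevant mean difference in degree" of reduction of 1.6 per week, two-sided at 0.05.

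The schedule in the Randomization Visit section is week 0, week 1, and then subjects "return for study visits every two weeks thereafter, at weeks 3, 5, 7, 9, 11, 13, 15, and 17". That makes 10 visits including baseline and 9 after it.

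The Endpoints section defines the primary endpoint as the change from week 0 to week 17. Statistical Methods, Primary analysis, fits time as a categorical factor, "with the 17-week time point as our primary ITT test", and treats all other contrasts as exploratory. Baseline covariates are to be "variables that have been established to be associated with the outcome based on prior literature". Sex and age are named; baseline binge count is not.

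The note at the end of the primary analysis keeps the analysis plan unchanged with 36 participants in place of 152. No section gives power, detectable difference or expected precision for 36.

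**The concern.** Ten assessments and an intraclass correlation raise power in a compound-symmetry calculation when the treatment effect is averaged over visits. A contrast at one visit does not get that gain. The sample size section describes its covariance structure as in line with the primary analysis. That is true of the covariance but does not settle the contrast.

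If the 80% belongs to an averaged effect, a reader will credit the primary test with a power that the plan's inputs do not give it. The cut to 36 ends any question of enlarging the trial, but the text still asserts 80% and keeps the same primary test. It also leaves the reader without any statement of what 36 participants can show.

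**Working it through.** **Inputs.** From Sample Size Calculation: difference 1.6, SD 4.1 (ratio 1.6/4.1 = 0.39, as stated), rho 0.59, compound symmetry, 10 assessments, two-sided alpha 0.05, 132 analysable. Allocation is 1:1 (Randomization Visit), so 66 per arm.

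**Formula.** n per arm = 2(1.96 + 0.8416)² × 4.1² × f / 1.6² = 103.08 × f, where f is the variance of the tested quantity divided by 4.1². Power = Φ(1.6/SE − 1.96), with SE = 4.1 × √(2f/n).

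**Reproducing the plan's figure.** For an average over k visits, f = (1 + (k−1) × 0.59)/k.
- k = 10: f = 0.631, n = 65.04 per arm; power at 66 is 80.6% (80.0% by noncentral t).
- k = 9: f = 0.6356, n = 65.51 per arm; power at 66 is 80.3% (79.7% by t).

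Both round up to 66 per arm, which is 132. A first-order autoregressive structure with rho 0.59 would give 97–98% at 66 per arm, so it does not fit.

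**Week-17 contrast.** The section does not say whether 4.1 is the SD of the reduction or of the weekly count, so each reading is shown.

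| Reading of 4.1 | f | n per arm for 80% | Power at 66 per arm (z / t) | Detectable at 80% |
|---|---|---|---|---|
| SD of the reduction | 1 | 103.1 | 61.1% / 60.5% | 2.00 |
| SD of weekly count, change score | 2(1−0.59) = 0.82 | 84.5 | 69.7% / 69.1% | 1.81 |
| SD of weekly count, baseline-adjusted | 1−0.59² = 0.652 | 67.2 | 79.3% / 78.7% | 1.61 |

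**Partial data.** The Missing data section keeps all collected visits, so the mixed model was also evaluated by generalised least squares. It used 76 per arm and 15% dropout, with the timing assumed. With dropout spread evenly:
- reduction: SE 0.697, so 1.6/0.697 − 1.96 = 0.336, or 63%;
- change score: SE 0.634, or 71%;
- common-baseline model: SE 0.572, or 80%.

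Over the dropout timings tried, the first two range over 60–64% and 70–72%.

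**Break-even SD.** The SD of the reduction that gives 80% at 66 per arm is 1.6/(2.8016 × √(2/66)) = 3.28. The change SDs quoted in the background for the lisdexamfetamine and sibutramine trials run from 1.52 to 2.3.

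**At 36.** The split is not given, so 18 per arm with complete data is assumed. SE = 4.1 × √f / 3.

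| Reading of 4.1 | SE | Power (z / t) | Detectable at 80% | 95% half-width (z / t) |
|---|---|---|---|---|
| SD of the reduction | 1.367 | 21.5% / 20.6% | 3.83 | 2.68 / 2.78 |
| Weekly count, change score | 1.238 | 25.2% / 24.2% | 3.47 | 2.43 / 2.52 |
| Weekly count, baseline-adjusted | 1.103 | 30.5% / 29.1% | 3.09 | 2.16 / 2.24 |

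**Attrition.** 152 × 0.85 = 129.2, not 132. The printed 152 agrees with 132 × 1.15 = 151.8, whereas 132/0.85 = 155.3. The effect is small: averaged power at 129 is 79.7%.

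**The case against.** The plan may deliver its 80% after all. The covariate clause is open, and baseline binge count is an obvious candidate for it. If 4.1 is a weekly-count SD, that adjustment restores about 79–80%. This stands, but only under that reading of 4.1. The plan neither names nor excludes the adjustment, and such a calculation would need 68 per arm (136) and would make no use of the 10 assessments.

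The SD of 4.1 may also be too large. The change SDs quoted in the background are all well under the break-even of 3.28, and with SDs of that size the week-17 test would have ample power at 132. This also stands, so the shortfall is conditional. But 4.1 is the plan's own input. Two trials are cited as sources, yet the text does not explain why 4.1 was preferred to the 1.52–2.04 quoted for one of them.

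Planned power can also be called moot now that recruitment has stopped. It can no longer change the sample, so what remains is a matter of correct reporting.

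Three stronger readings are tempting and are not supported.
- A reader might infer that the calculation certainly was time-averaged. The text never says so. The label averaged over visits is not safe either: if 4.1 is a weekly-count SD, the averaged change from week 0 has f = 0.6356 + 1 − 1.18 = 0.456, and power at 66 per arm is about 91%, not 80%.
- A reader might infer that the week-17 test was underpowered whatever the assumptions. The two points above rule that out.
- A reader might infer that settling what 4.1 measures decides how a null result at n=36 is read. Every reading of 4.1 gives a half-width above 1.6. Only replacing 4.1 with the smaller quoted SDs brings it to 1.2–1.4, and a finished trial is read from its observed interval.

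**Conclusion.** The concern holds in a conditional form. The documents do not show that the primary week-17 test has the stated 80% power. With the plan's inputs and no baseline adjustment it has about 61% (SD of the reduction) or 70% (weekly count, change score) at 66 per arm, and at most about 64% or 72% with partial data from 76 per arm. It reaches 79–80% only under the weekly-count reading with baseline adjustment.

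At 36 the planning figures are 21–25% power, or 29–31% baseline-adjusted. The half-width of 2.2–2.8 episodes exceeds the 1.6 that the plan calls clinically relevant. Complete data is a favourable assumption, because the note of 5.20.19 shows that the 36 include drop-outs.

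All figures assume an untransformed outcome and compound symmetry; the plan allows a shifted log and other structures. The attrition slip is minor. This should be fixed, as a misstated power and a missing statement of precision. It does not invalidate the analysis.

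**What to change.** Make these changes before unblinding, in wording only:
1. State whether 4.1 is the SD of the reduction or of the weekly count, and why it was chosen. State which contrast the 80% describes, confirmed from the original PASS run and not asserted to be time-averaged.
2. Replace the 80% with the power or detectable difference for the week-17 contrast at 132 and at 36. Give the SD, baseline handling, covariance and missing-visit assumptions used.
3. Correct the number remaining after 15% attrition from 152 to 129.
4. State that the week-17 group difference will be reported with a 95% CI, and that a non-significant result will be read from the observed interval. For the primary outcome the plan now promises mean (SE) change by group, while for remission it already promises 95% CIs for the group comparison.

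The cost is a less favourable stated power. No patients are added, and the endpoint, model and dataset do not change.
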